We propose the implementation and testing of a novel, highly efficient pragmatic intervention that seeks to shift the clinical practice paradigm of emergency medicine. We propose a pragmatic, cluster-randomized stepped wedge design to test the effectiveness of primary palliative care education, training, and technical support for emergency medicine (PRIM-ER) in 35 Emergency Departments (EDs). PRIM-ER includes four core components: 1) evidence-based multidisciplinary primary palliative care education, 2) simulation-based workshops on communication in serious illness, 3) clinical decision support, and 4) provider audit and feedback. These core components will be implemented in each participating health system as part of a quality improvement initiative to improve the care older adults with serious illness receive in the ED setting. In the UG3 phase of the project, we will: 1) tailor PRIM-ER to the emergency provider workforce and a more diverse ED context using an agile implementation framework approach; and 2) pilot test PRIM-ER at two sites for feasibility, fidelity, and usability. In the UH3 phase, we will: 3) implement PRIM-ER in a cluster-randomized, stepped wedge design in the remaining 33 EDs; and 4) measure the effect of PRIM-ER on aspects of: a) ED disposition to an acute setting; b) healthcare utilization in the 6 months following the ED visit; and c) survival following the index ED visit. The project will thus be implemented in a total of 35 EDs (2 pilot sites and 33 remaining EDs) as previously approved and outlined in the below table. We hypothesize that it will be feasible to test PRIM-ER at two EDs with a high level of fidelity and usability and implement at all sites. We also hypothesize that older adult visitors with serious, life-limiting illness cared for by providers with primary palliative care skills will be less likely to be admitted to an inpatient setting, more likely to be discharged home or to a palliative care service, and will have higher home health and hospice use, fewer inpatient days and ICU admissions at 6 months, and longer survival than those seen prior to implementation. Additionally, we hypothesize that sites with higher baseline ED disposition to an acute care setting and less primary palliative care knowledge and skills will demonstrate greater change after implementation.

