For the research component of the study, we will use Medicare claims of the beneficiaries in our patient cohort to measure outcomes, including ED disposition to an acute care setting, healthcare in the 6 months following the ED visit and survival following the index ED visit as a result of the intervention. The patient cohort will be extracted via the Centers for Medicare and Medicaid Services (CMS) Research Data Assistance Center (ResDAC) using a two-step process to maximize diversity, and minimize intentional or unintentional exclusions based on risk, age, health literacy, demographics, or expected adherence. First, we will provide a comprehensive list of facility codes for the 35 participating EDs. Inpatient and ambulatory claims will be used to identify community-dwelling ED visitors 66 years and over who made a visit to any of the EDs from 2 years prior to study initiation until the last day implementation day of PRIM-ER. ED claims will be identified via Revenue Center Code values of 0450-0459 (Emergency room) or 0981 (Professional fees-Emergency room) according to ResDAC. We will then examine all inpatient, ambulatory, and carrier claims for the 12 months prior to each older adult's index ED visit to calculate each beneficiary's Gagne Index, a score developed to predict one-year mortality in community-dwelling older adults.²⁴ The Gagne Index has been adapted from the Romano-Charlson Index and the Elixhauser system.^{25,26} It calculates a score based on the presence or absence of ICD-9s from inpatient and ambulatory claims in the prior year. Beneficiaries with a one-year mortality of at least 30% (score > 6) based on claims from the previous 12 months will be included in the analysis.

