We will conduct an exploratory analysis to examine if access to home and community health services predicts healthcare utilization in the 6 months after an ED visit at the end of life. We will examine correlations between home and community health access factors and healthcare utilization from the 18 healthcare systems included in the PRIM-ER study using the Senior Care Services Scale (SCSS) developed by Arbaje et al.³² Data from all 18 healthcare systems collected from the Grey Literature Review and Qualitative Interviews will be eligible for this exploratory analysis.

Contextual factors from the Grey Literature Review and the Qualitative Interviews will be used to analyze if access to home and community health services predicts healthcare utilization. Healthcare utilization data will be provided from the PRIM-ER study and will be collected from Medicare claims data to include ED revisits (count), inpatient days (count), home health use (Yes/No), and hospice use (Yes/No) in the 6 months from the index PRIM-ER ED visit. These measures of healthcare utilization are based on the Dartmouth Atlas Decedent Cohort Care Intensity Measures to monitor the quality of end-of-life care in Medicare patients. The SCSS will be adapted to PRIM-ER using contextual factors from the Grey Literature Review and Qualitative Interviews 2. Each healthcare system will be assigned a score based on their access to home and community health services.

B) Inclusion and Exclusion Criteria

Eligible patients will include ED patients 66 years or older with serious, life-limiting illness who visited any of our EDs during the implementation of PRIM-ER. Patients must demonstrate one-year mortality of at least 30 percent (score > 6) according to the Gagne Index, a validated instrument used to measure all cause one-year mortality in community-dwelling older adults, calculated based on their prior 12 months before the index ED visit of Medicare claims. ED patients transferred from a nursing home on the index ED visit will be excluded since prediction of mortality and disposition of such patients differs from community-dwelling adults. Patients currently receiving hospice at the time of the index ED visit will also be excluded since they have already received services.

Qualitative Interviews Contextual Assessment

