We will recruit our participants for the provider interviews through a combination of word-of-mouth and email invitation through the healthcare systems points of contact established via the PRIM-ER study. After a participant expresses interest in participation, they will be contacted by [name] for Contextual Assessment or Senior Research Project Manager ([name]) or Co-Investigator [name] for CDS interview for an expanded explanation of the study, study procedures, their role as a participant, and potential risks and benefits. It will be clearly disclosed that the interview will occur via ZOOM teleconferencing and be recorded. Once the participant is read all study materials and information and had a chance to have all their questions answered, the recording device will be started, and the provider will be asked to provide verbal consent for participation. All qualitative interviews for this project, will follow the same protocol as outlined here.

E) Data Analysis

a. Dependent variables

ED disposition will be measured on the index ED visit, and will be a dichotomous variable for an acute care admission (Yes/No). Acute care admission will be defined as admission to a non-palliative service, and non-acute care admission will include admission to a palliative care service or unit, discharge to home, observation (without a change to inpatient status), or transfer to inpatient or outpatient hospice.

Healthcare utilization will be measured as ED revisits (count), inpatient days (count), home health use (Yes/No), and hospice use (Yes/No) in the 6 months from the index ED visit. These will be identified through revenue codes in each site's administrative data. We developed these measures of healthcare utilization based on the *Dartmouth Atlas Decedent Cohort Care Intensity Measures* to monitor the quality of end-of-life care in Medicare patients with serious chronic illness. ²⁸⁻³⁰

Survival will be measured in days from the index ED visit to death or 6 months, whichever is sooner.

b. Independent variables

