Table 1 outlines the independent variables. Independent variables were previously assessed at the time of site implementation. Healthcare system- and provider-level variables were collected by the project manager and via a provider survey at the level of each participating ED. Patient-level variables will be assessed using the CMS Research Data Assistance Center Master Beneficiary Summary File, Base (A/B/D) Segment. The Project Manager will also document if trainings occurred via in-person or virtually to understand more deeply the implementation of the QI initiative at each site.

Table 1. Independent Variables			
Variable	Coding	Source	
Implementation Period	Weeks from Time 0	Project Manager	
Healthcare system/ED-level variables			
Health System	Allegheny, Bay State, Beaumont, Brigham and Women's, Christiana Care, Henry Ford, [name] Anderson, NYU Langone, Ohio State University, Ochsner, Rutgers, Sinai, UC San Francisco, University of Florida, University of Pennsylvania, University of Utah, Yale New Haven	Project Manager	
ED	1—35	Project Manager	
ED Volume	30,000—49,999 visits, 50,000—69,999 visits, 70,000—89,999 visits, ≥ 90,000 visits	Project Manager	
Ownership	Nonprofit, Government, For Profit	Project Manager	
Emergency medicine residency training site	Yes/No	Project Manager	
Free-standing ED	Yes/No	Project Manager	
Dedicated ED social worker/care manager	Yes/No	Project Manager	
US Region	Northeast, Midwest, Southeast, Southwest, West	Project Manager	
Metropolitan Status+	Yes/No	Project Manager	
Outpatient palliative care	Yes/No	Project Manager	
EHR	Epic, Cerner	Project Manager	
Trauma center	Yes/No	Project Manager	
Patient variables			

Age	Years	Master Beneficiary Summary File, Base Segment
Gender	Female, Male, Other	Master Beneficiary Summary File, Base Segment
Race/Ethnicity	Asian, Black, Hispanic, White, North American Native, Unknown, Other	Master Beneficiary Summary File, Base Segment
Gagne index ²⁴	Count of conditions	Inpatient and outpatient RIF
+Population estimates by MSA are based on estimates of the civilian non-institutionalized population of the US as of July 1, 2013, from the 2013 National Health Interview Survey, National Center for Health Statistics, compiled according to the 2013 Office of Management and Budget definitions of core-based statistical areas. See http://www.census.gov/population/metro/ for more about metropolitan statistical area definitions.		

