Prior to conducting the outcome analyses, we will compare patients in each ED cluster with respect to patient, provider, and facility characteristics. We will assess whether any adjustments will need to be made in the final statistical models based on whether the differences are clinically meaningful. To account for nesting in the data structure (patients nested in hospitals), we will use mixed effect multi-level models to estimate effect sizes. We anticipate two sources of variation.

The **primary outcome** is the proportion of eligible patients whose disposition is to an acute care setting (inpatient, non-palliative service). The **secondary outcomes** include healthcare service utilization in the 6 months following the ED visit and survival times following the ED visit. The health utilization outcomes include receipt of ED revisits (count), home health services (yes/no), inpatient days (count), admission to an ICU

(yes/no), and admission to hospice (yes/no). The analysis of the effect of PRIM-ER on ED disposition in the context of a stepped-wedge design will be based on a Generalized Linear Mixed Model (GLMM). In particular, to assess the intervention effect, we will use a generalized linear binomial model with random site level effects. The analysis of site, provider, and patient-level characteristics that are associated with variation in impact of PRIM-ER will be based on extending the models used in the analysis plan for ED disposition, healthcare utilization in 6 months following the ED visit, and survival times to include independent variables related to the characteristics of interest.

5. Risks to Subjects

Any information collected from Emergency Department providers will be utilized solely for QI purposes and not analyzed for research.

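### The home health outcome counts any use in 6 months, and nothing in the plan separates or adjusts for patients already receiving home health at the index visit

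*Combined protocol and SAP*

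**What the plan says.** Under Dependent variables (Data Analysis, part a) the home health outcome is binary and counts any use: "home health use (Yes/No), and hospice use (Yes/No) in the 6 months from the index ED visit". The Methods (part c) list it again as a yes/no secondary outcome. The opening statement of hypotheses expects that patients seen after implementation "will have higher home health and hospice use".

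The Inclusion and Exclusion Criteria treat the two services differently. For hospice: "Patients currently receiving hospice at the time of the index ED visit will also be excluded since they have already received services". The only other care-setting exclusion is that "ED patients transferred from a nursing home on the index ED visit will be excluded". Patients with home health in place at the index visit remain eligible.

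No other text identifies them. To compute the Gagne Index, the study team will "examine all inpatient, ambulatory, and carrier claims for the 12 months prior" to the index visit; home health claims are not named there. The Home Health file is named for monitoring outcomes up to 6 months after index. At patient level, Table 1 lists age, gender, race/ethnicity and the Gagne index. The 12-month roll-in decides when baseline outcome rates start to count. It does not record a patient's service status at index.

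**The concern.** A patient with a home health episode open on the index date will often have a home health claim soon afterwards, whatever the ED does. That patient is scored Yes, and the Yes says more about status on arrival than about the visit. To the extent that PRIM-ER works by prompting new referrals, such patients add to numerator and denominator in both periods and pull the before-after difference towards zero.

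The hospice outcome largely avoids this, because current hospice patients are not in the cohort. The two services share one directional hypothesis, yet one is measured in people not currently receiving it and the other in a mix of recipients and non-recipients, with no explanation. A reader of the results could not tell a weak effect on referral from a stronger effect diluted by existing use. The variable is also reused in the exploratory contextual analysis, where use that began before the visit would count as use after it.

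**Working it through.** **Nothing to reproduce.** The plan gives an expected count of more than 57,000 patients (Number of Subjects). It gives no home health rate, prevalence at index, target effect, alpha, power or intracluster correlation. The values below are assumptions chosen to show direction and range.

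**Inputs (all assumed).** q = share on home health at index: 15%, 25%, 35%. New-start rate among the rest: s0 = 30% before and s1 = 35% after implementation, odds ratio (0.35/0.65)/(0.30/0.70) = 1.26. c0, c1 = share of current users with a home health claim after index, before and after implementation.

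**Formula.** Observed any-use rate = q·c + (1−q)·s. Observed difference = q·(c1−c0) + (1−q)·(s1−s0).

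**Step 1: current users do not respond, c0 = c1 = 100%.**

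| q | Before | After | Difference | Odds ratio | Current users among Yes, before |
|---|---|---|---|---|---|
| 15% | 40.5% | 44.75% | 4.25 points | 1.19 | 15/40.5 = 37% |
| 25% | 47.5% | 51.25% | 3.75 points | 1.16 | 25/47.5 = 53% |
| 35% | 54.5% | 57.75% | 3.25 points | 1.14 | 35/54.5 = 64% |

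The shrinkage needs c1 = c0, not c = 100%. With q = 25% and c0 = c1 = 70% or 85%, the difference is still 0.75 × 5 = 3.75 points.

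**Step 2: information.** Take information as (patients × difference²)/[a(1−a) + b(1−b)], where a and b are the rates before and after. R is the information from new starts in the (1−q) share of patients, divided by that from any use in everyone. At q = 25%:

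- new starts: 0.75 × 0.0025/0.4375 = 0.00429
- any use: 0.001406/0.4992 = 0.00282
- R = 1.52

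At q = 15% and 35%, R = 1.31 and 1.73.

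**Step 3: let current users respond (q = 25%, c0 = 80%).**

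| c1 | Any use, before to after | Difference | R |
|---|---|---|---|
| 80% | 42.5% to 46.25% | 3.75 points | 1.50 |
| 83% | 42.5% to 47.0% | 4.5 points | 1.04 |
| 85% | 42.5% to 47.5% | 5.0 points | 0.85 |

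If current users gain the same 5 points, nothing is lost, and restricting to non-users discards information.

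**Step 4: is detection at risk?** Ignoring clustering and time, with 57,000/2 = 28,500 patients per period, the any-use comparison in Step 1 gives z of about 10.3, 9.0 and 7.8. On that simplified basis detection is not in doubt; the reported effect size is what changes. A stepped-wedge calculation would give smaller values, but the documents supply no inputs for one.

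**The case against.** Any use is a legitimate utilisation measure. The hypothesis speaks of use, not of starts, so outcome and hypothesis agree, and replacing one by the other would change the estimand. This stands, and it is why any use should remain the secondary outcome.

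A reader might infer that current users are certain to be scored Yes and that PRIM-ER can affect only new starts. The documents say neither. A current user may die, be admitted or move to hospice before another home health claim. The intervention includes spreading information on local home care and hospice, so it could affect whether existing care continues. Step 3 shows that the gain from restriction depends on this.

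A reader might also infer that the hospice exclusion exists to make the hospice outcome one of new use, so that leaving home health alone is a contradiction. The exclusion is a cohort criterion covering every outcome, and it removes current hospice patients only, not past users. The contrast is unexplained, but it is not a contradiction.

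Finally, a reader might infer that differences in prior home health use between EDs or calendar periods pass straight into the result. The planned models have random site effects, which address stable differences between EDs. Table 1 lists implementation period in weeks. The Methods also plan a comparison of patients across EDs, with adjustment where differences are clinically meaningful. That clause is discretionary and does not name prior home health. What remains is a shift in prior use within an ED beyond the time trend, and the documents give no reason to expect one.

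**Conclusion.** The gap is real but limited. The plan neither identifies patients on home health at the index visit nor adjusts for them, so an outcome expected to rise mixes existing use with new use. If current users respond little, the absolute difference is multiplied by about (1−q): 4.25, 3.75 or 3.25 points instead of 5 in the illustration. If they respond equally, there is no loss. Both the prevalence and the response of current users are unknown from the documents, so no single figure can be attached to this trial.

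The main consequence is dilution and an effect that is hard to interpret. Bias would need a within-ED change in prior use that site and time terms do not absorb. One secondary outcome and its reuse in the exploratory analysis are affected; the primary outcome is not. The documents do not support calling the any-use definition wrong. They support recording baseline status and using it.

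**What to change.** - Extend the Home Health file, already named for outcomes, to a short pre-index window of stated length, and flag each patient with home health open on the index date. State the rule that defines open.
- Add the flag to the patient variables in Table 1 and to the home health model as a baseline covariate.
- Keep any use in the full cohort as the secondary outcome, and say that any use is intended.
- Pre-specify new home health start within 6 months among unflagged patients as a companion analysis. It is needed because adjusting for the flag improves precision but does not undo the (1−q) factor in a full-cohort risk difference.
- Report the share flagged, by ED and by period.
- Name the claims source for this outcome. Dependent variables refers to each site's administrative data, while the study design and Data Collection text name the Medicare Home Health file.

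The cost is a further claims look-back, which the current plan does not request for the pre-index period, and one extra analysis on a subset. No patient leaves the cohort and the primary analysis does not change.

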This is a cluster-randomized QI initiative that will implement and test the impact of PRIM-ER in various healthcare settings. We will first develop and pilot test the QI initiative at two sites in the UG3 phase, and then use a cluster-randomized, stepped wedge design to implement the education, training, and technical support in our network of EDs in the UH3 phase. Randomization will occur at the ED level and be done in advance by the biostatistician to determine the order in which the training will occur. Due to the COVID-19 pandemic, training will occur either in-person or virtually. The virtual trainings will occur using NYULH's Zoom account, meeting ID and set password. A member of the PRIM-ER team will be on each virtual training in order to monitor learner's attendance and assist with any technical glitches. The PRIM-ER team will provide the training link, meeting ID, and password to each Site Principal Investigator (PI) and the Site PI will distribute the link and meeting ID accordingly to his/her staff at their own home institution. Reminder e-mails about the training will be sent from each Site PI to his/her staff. The overall approach involves ongoing asynchronous learning and technical support to bolster skills, conduct interdisciplinary case reviews, and reinforce clinical pathways and protocols via provider audit and feedback. Electronic triggers for palliative care will be embedded in the electronic health record (EHR) to identify patients who may benefit from hospice or palliative care services. These electronic triggers already existing in the Perelman Center for Emergency Services EHR as part of standard, clinical workflow, but will be further tailored for each participating health system. Palliative care champions at each site will facilitate attendance at didactic and workshop sessions, disseminate information about local resources for outpatient palliative care, home care and hospice, and work with the local informatics team to reinforce protocols and implement trigger criteria to identify older adults who may benefit from further needs assessment and follow-up. We will engage with the palliative care champions to better understand the QI implementation process including but not limited to obtaining champion's feedback on the initiative, suggestions for improvements, and adaptations- all which are common approaches in implementing and reflecting on QI initiatives. Engagement will be in the form of discussions post QI about what went well, and what can be improved upon in moving forward as well as understanding from the champion's perspective what they could have done differently so the project team can gather lessons learned. Physicians and nurses will receive audit and feedback reports to monitor their performance over time, and a learning monitoring system will track participation in educational activities.

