For the PRIM-ER Contextual Assessment that data analysis will vary per specific component.

Grey Literature Review: Data will be collected and analyzed on the regional, state, and healthcare system level. Data will be coded and collated per topic of interest. A combination of descriptive statistics, narrative description, and thematic coding will be used to summarize and present the data.

Qualitative Interviews: For the qualitative data, the interview transcriptions will undergo verbatim transcription and thematic coding. We will develop deductive codes based on the discussion guide, and inductive codes based on salient topics identified during review and coding of the transcripts. We will compare codes across all of the transcripts during the final analysis phase and condense codes into meaningful categories. We will use ATLAS.ti software to facilitate coding as well as cross-investigator and cross-interview analyses. We will also develop data matrices to highlight prominent themes related to facilitators and barriers to home and community health services. For quantitative analysis, we will use descriptive statistics to summarize the data.

Exploratory Analysis: This exploratory analysis will mirror the healthcare utilization analysis and statistical model described in the PRIM-ER. Each healthcare system index score will be used as an independent variable in our predictive model to determine the relationship between home and community health access factors and healthcare utilization in the 6 months after an ED visit at the end of life.

The healthcare system dependent (Ea.) and independent variables (Eb.) described above for PRIM-ER grant will also be used for the analysis of the PRIM-ER Contextual Assessment.

c. Methods

The analytic plan accounts for the nested structure of the data, assesses normality assumptions of dependent variables, and addresses issues related to missing data, study participation bias, and baseline covariate balance. We address each of these in turn. All analyses will be conducted in R 3.3.2 (R Foundation for Statistical Computing, Vienna).

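### The exploratory access score varies only between health systems (at most 18), but the stated clustering is most naturally at ED level, so the score's interval may be too narrow

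*Combined protocol and SAP*

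**What the plan says.** The Exploratory Analysis section that precedes the inclusion criteria defines the predictor: "Each healthcare system will be assigned a score based on their access to home and community health services". It also announces a simpler look at the data: "We will examine correlations between home and community health access factors and healthcare utilization from the 18 healthcare systems".

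Under Data Analysis (E), the Exploratory Analysis paragraph states the model: "This exploratory analysis will mirror the healthcare utilization analysis and statistical model described in the PRIM-ER". The score enters it as follows: "Each healthcare system index score will be used as an independent variable in our predictive model". The next paragraph carries the parent study's variables over: "The healthcare system dependent (Ea.) and independent variables (Eb.) described above for PRIM-ER grant will also be used". Table 1, which lists those independent variables, includes both Health System and ED and does not say how either enters a model.

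Methods (E.c) gives the clustering: "To account for nesting in the data structure (patients nested in hospitals), we will use mixed effect multi-level models". It adds "We anticipate two sources of variation" without naming the two. The only random effect named is at site level, in the ED disposition model. I found no health-system random effect, no system-clustered standard error and no small-cluster correction.

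**The concern.** The level of clustering has to match the level at which the predictor varies. For the intervention it does, because "Randomization will occur at the ED level". The access score sits one level higher and is the same for every ED in a system. If the copied model has only an ED intercept, any system-to-system variation left after the score and covariates is treated as independent ED noise, and the standard error of the score is too small.

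At stake is the interval for the relationship between access and utilization, which could look more precise than 18 systems allow. The large patient count does not help, because the limit is the number of systems.

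**Working it through.** The plan states no power, precision, intraclass correlation or alpha for this analysis, so there is no figure to reproduce. I use 5% only as a yardstick.

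**Inputs from the documents.** 35 EDs; 18 health systems; over 57,000 patients; four EDs under the first system in the site table (Settings of the Human Research). The rest of that table is not visible.

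**Assumed.** The share of residual between-ED variance that lies between systems (rho: 0, 10, 25, 50%); the layout beyond the first system; a normally distributed score with no true effect.

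**Patients per ED.** 57,000 / 35 = 1,629. With an assumed intraclass correlation of 0.02, within-ED variance is 0.98 / 0.02 = 49 times the between-ED variance. The sampling variance of an ED mean is then 49 / 1,629 = 0.03 of the between-ED variance. The analysis behaves like a regression on 35 ED means.

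**Layouts** (18 systems, 35 EDs, first system fixed at four):
- A, most even: 4, then 14 systems of 2 and 3 of 1. Sum of squared sizes 16 + 56 + 3 = 75.
- B, moderate: 4, 4, 4, 3, 3, 3, 2, 2 and 10 of 1. Sum 48 + 27 + 8 + 10 = 93.
- C, most uneven: 15, 4 and 16 of 1. Sum 225 + 16 + 16 = 257.

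**Rough formula.** Variance inflation = 1 + (m_w - 1) x rho, where m_w is the sum of squared sizes divided by 35.
- A: m_w = 75 / 35 = 2.14. At rho = 0.25, 1 + 1.14 x 0.25 = 1.29, so the SE is too small by a factor of 1.13. At 0.50, 1.57, factor 1.25.
- B: m_w = 93 / 35 = 2.66. Factors 1.19 and 1.35.
- C: m_w = 257 / 35 = 7.34. The formula gives 1.61 and 2.04, well above the simulated values below, so I rely on the simulation for that layout.

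**Simulation** (300,000 runs per cell, ED-only regression, t on 33 df, no covariates): type I error, with the SE factor in brackets.

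| System share | A | B | C |
|---|---|---|---|
| 0% | 4.9% (1.00) | 5.0% (1.00) | 4.9% (1.00) |
| 10% | 6.2% (1.06) | 6.8% (1.07) | 8.1% (1.11) |
| 25% | 8.3% (1.14) | 9.5% (1.18) | 12.8% (1.26) |
| 50% | 12.0% (1.26) | 14.4% (1.34) | 20.1% (1.50) |

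In 400 random layouts the median error was 5.0, 6.8, 9.6 and 14.2%.

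**With a system-level covariate.** Adding the five-level Region from Table 1, taken as constant within systems (35 - 2 - 4 = 29 df; 6,000 runs), gives 8.3-9.2% at a 25% share and 13.3-14.5% at 50% across A to C. The high end of layout C disappears.

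**Yes/no and count outcomes.** A two-stage approximation of logistic and negative binomial mixed models (layouts A and B, 1,500 runs; event rate, mean count, variance and ED sizes assumed) gives 4.7-5.8% at zero share, 9.1-10.4% at 25% and 10.3-13.7% at 50%.

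**Health System as a fixed factor.** Eighteen system indicators have rank 18. Adding the score leaves the rank at 18, because the score is a linear combination of the indicators. Its coefficient is then not estimable.

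**The case against.** The strongest reply is that the plan never fixes the level. *Site* usually means an ED: the project summary and the study design description use it for the two pilot EDs and the other 33. But the text on the CDS interviews and on the Steering Committee ties a site principal investigator to each health system. If the site effect is a health-system effect, the needed clustering is already there. Likewise, if Health System from Table 1 enters as a random factor, the problem is solved. If the correlations across systems use one value per system, that part is sound.

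This stands in part. A reader might infer that the plan has definitely chosen the wrong level; the documents do not support that. The ED reading is still the more natural one, since the site effect comes in the same Methods text that names hospitals as the clusters. The correlations are a separate step from the model that takes the score as a predictor.

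A reader might also infer from layout C that the error is 20% and the SE is understated by half. That needs one system to hold 15 of the 35 EDs and no system-level covariates. Nothing visible suggests such a layout, and the plan carries Table 1 covariates into this analysis.

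Finally, the analysis is labelled exploratory and has no stated decision rule. That limits the importance but does not remove the mismatch.

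**Conclusion.** The point holds on the natural reading of the plan and is conditional. With ED-level clustering only, the score's interval is too narrow whenever outcomes vary between systems beyond the score and covariates. With no such variation there is no error. As an illustration, a nominal 5% test has an error of roughly 8-10% at a 25% system share and 12-15% at 50%. In the runs, clearly higher values came only with EDs spread very unevenly and no system-level covariates. These figures rest on an assumed share, layout and score distribution; they are neither bounds nor properties of this plan.

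Nothing here reaches the primary or secondary intervention effects: the intervention is randomized by ED, and ED-level clustering fits it. Nor do the documents show that the score is inestimable. That follows only if Health System (or ED) is entered as a fixed factor, which Table 1 leaves open. This is an optional improvement to an exploratory analysis.

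**What to change.** In the Exploratory Analysis paragraph under Data Analysis (E), state three things.

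1. Inference on the access score is at health-system level. The model has a health-system random intercept above the ED random intercept, with a t reference on (systems analysed - 2 - parameters for covariates constant within systems) degrees of freedom. With 18 systems that is 18 - 2 = 16 with no such covariate, 16 - 4 = 12 with a five-level Region, and 11 if a two-level EHR is added, provided these are constant within systems. An analysis of system-level summaries is an acceptable alternative.
2. Health System and ED are not fixed factors in this model.
3. Whether the correlations announced earlier use one value per system.

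In the runs, the random intercept gave 3.6-6.3% error at 25-50% shares on 16 df, and system means gave 4.6-5.8% at all shares. The system means were checked on linear ED-level data only. System-constant covariates should be few, since each parameter uses one of the 16 degrees of freedom.

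The cost is a few sentences and no new data. Intervals become wider: the multiplier alone rises from 2.03 (33 df) to 2.12 (16 df), or 2.18 on 12 df. If there is no residual system variance, the random-intercept version is slightly conservative (3.1-4.1% error in the yes/no and count check).
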